1.5 Study Rationale and Risk/Benefits

1.5.1 Study Rationale

Recent advances in the endoscopic bariatric therapies (EBTs) provided an alternative effective and minimally invasive treatment approach to obesity that would increase treatment options beyond surgery, medications, and lifestyle measures. Due to the special ethical consideration of involving minors in empirical therapies, the reversible EBTs might be more viable option for managing obesity in adolescents and prevent long-term complications. One of the EBT approaches is the intragastric balloon (IGB) which involves an endoscopic device for temporary nonpharmaceutical and nonsurgical treatment for morbid obesity.[23] The Orbera Intragastic Balloon (IGB) (Apollo Endo-surgery, Austin, TX) is an elastic spherical balloon made from silicone, filled with about 600 ml of saline and is placed in the stomach via upper endoscopy. The IGB is designed to stay in place for 6 months prior to endoscopic removal. The Orbera IGB was approved for use in adults in August of 2015. The IGB has been widely used in Europe, South America, and the Middle East with excellent safety profile. A recent review and metaanalysis by Abu Dayyeh et al, of 8506 IGB implantation showed that IGB resulted in significant weight loss (up to 15%) with serious adverse events rate of 0.3-0.1% mostly in patient with prior gastric surgery.[24] Recent trials in adolescents with obesity have confirmed the safety and feasibility of using the IGB as a weight management tool in adolescents with morbid obesity.[15, 16] As discussed above, IGB could also be useful in treating NAFLD, NASH and DM2 in adolescents.

1.5.2 Anticipated Risks

The rates of adverse events after implantation of the Orbera balloon are pooled from a manual review of 68 studies (8500 implantations) and are summarized in Figure 1. Pain and nausea are frequent side-effects after Orbera balloon implantation, occurring in up to 33.7% of subjects. Medications such as proton pump inhibitors, antispasmodic drugs, and antiemetics are usually prescribed prophylactically before, during, and after balloon placement to prevent or minimize these expected common side effects. Serious side-effects with Orbera balloon are rare with an incidence of migration and gastric perforation of 1.4% and 0.1%, respectively. Most of the reported perforations with the Orbera were in patients who had undergone previous gastric surgeries, which is a contraindication for use in the US.[18]

[figure not shown]

Figure 1. Pooled Orbera Complications from 68 studies (8500 patients) [24]

As with all endoscopic and/or implant procedures, serious injury or death can occur. With any device, there is always a chance of developing problems from the treatment. Not all risks or problems associated with the use of the Orbera Intragastric Balloon are known. Common risks that can occur include nausea, vomiting, abdominal pain, gastroesophageal reflux disease, and bad breath. This is expected due to the physical presence of the balloon in the subject's stomach. Anti-nausea medications may be given on the procedure day and should help with any nausea and vomiting that the subject may have. The side effects and risks of the medication the subject may be prescribed will be discussed with the subject by the study PI ([name]) prior to the balloon procedure.

Per the Orbera Directions For Use (revision 2), possible complications from the use of ORBERA IGB include:

- Intestinal obstruction by the balloon which could require surgery or endoscopic removal of the balloon
- Death due to complications related to intestinal obstruction
- Esophageal obstruction which could require surgery or endoscopic removal of the balloon
- Gastric outlet obstruction which could require surgical removal of the balloon
- Injury to the digestive tract during placement of the balloon in an improper location which could cause bleeding and perforation and in turn could require surgical correction
- Insufficient or no weight loss
- Adverse health consequences resulting from weight loss
- Gastric discomfort, feelings of nausea and vomiting following balloon placement

- Continuing nausea and vomiting or possibly the prevention of vomiting
- A feeling of heaviness in the abdomen
- Abdominal or back pain, either steady or cyclic
- Gastroesophageal reflux
- Influence on digestion of food
- Blockage of food entering into the stomach
- Bacterial growth in the fluid which fills the balloon which could cause infection, fever, cramps, and diarrhea
- Injury to the lining of the digestive tract as a result of direct contact with the balloon, grasping forceps, or as a result of increased acid production by the stomach which could lead to ulcer formation and possible surgical correction
- Death due to complications related to gastric or esophageal perforation
- Balloon deflation and subsequent replacement
- Acute pancreatitis
- Spontaneous over inflation

Possible risks which may occur from the subject's endoscopy procedure include difficulty swallowing, injury to the lining of the esophagus or stomach, perforation (a hole in the wall of your stomach or esophagus), bleeding, infection, inflammation, dental injury, pain following the procedure with the potential for hospitalization to control pain, post procedure fluid collection with or without abscess or death.

The risk of monitored controlled sedations medications used to make the subject drowsy can cause breathing difficulties or a drop in blood pressure. These side effects are easily observed and managed by the anaesthesia team. These medications may cause some inflammation at the intravenous site where the drugs are given again that will be discussed and explained by the anaesthesia team prior to the procedure.

If any gastric ulceration were identified at the time IGB removal after 6 months, subjects will be treated with proton pump inhibitors therapy with dose and duration of therapy determined by the study PI. These subjects will be followed clinically until complete resolution.

1.5.3 Potential Benefits

The Orbera intragastric balloon is expected to result in 12.3%, 13.16 and 11.27% total body weight loss (TBWL) at 3, 6, and 12 months after implantation, respectively, based on recent review.[18] This balloon is currently FDA approved for use in adults in the United States. Other potential benefits include improving the metabolic syndrome manifestation such as:

1. Sustainable decrease in baseline heart rate (>10 beats/min) and systolic blood pressure (>10 mmHg/hg)
2. Normalization of liver function panel
3. Decrease in fatty liver infiltration on liver ultrasound (US)
4. Decrease in Hg1Ac level

5. Improvement of fasting lipid profile
6. Increase in activity level

2 Study Objectives

Primary Objective:

Assess the safety and effectiveness of an intragastric balloon device in obese adolescent subjects with comorbidities to assist with weight reduction and reverse metabolic complications.

The intended use for the subject device (IGB) in adolescents is to induce > 10% total body weight loss in morbidly obese adolescents.

Specific Aims:

- Determine if placement of IGB for a period of 6 months is safe and results in weight loss and metabolic improvement in obese adolescents
- Determine if intragastric balloon is well tolerated by adolescents
- Determine if weight loss is sustainable after the IGB removal through integrating the subjects in the pediatric weight management program

Study Protocol Hypothesis:

Intragastric balloon is a safe, well tolerated and effective intervention for weight loss and decreasing obesity complications in adolescents with comorbidities.

3 Study Design

3.1 General Design

Potential subjects will be seen by a pediatric endocrinologist ([name]) or a pediatric gastroenterologist ([name]) who will review and approve the potential subject's inclusion and exclusion criteria. For interested subjects who have met all the inclusion and exclusion criteria, assent will be obtained from the subject and consent will be obtained from the parent/legal guardian. After consent, the subject will be given three questionnaires to complete at home and return at the baseline visit; the PN Q will be returned to and reviewed by the dietitian in the weight management clinic (WMC), and the CES-D and SCAS will be returned to and reviewed by the psychologist.

At baseline, subjects will be seen by the pediatric weight management multidisciplinary team consisting of a pediatric endocrinologist ([name]) or a pediatric gastroenterologist ([name]) for a physical examination; a registered dietitian in the WMC; and a psychologist. Blood, urine, and stool samples will be collected at baseline. Food record templates will be provided to study subjects to be completed for three days prior to each future WMC visit.

The baseline requirements may all be completed in one day, or they may be completed on separate days depending on scheduling times and the subject's availability. Female subjects will also have a urine pregnancy test in the morning before the procedure.

If the subject still meets all the inclusion and exclusion criteria after the baseline evaluations and the pregnancy test are completed, s/he will undergo physical examination followed by placement of the IGB by a gastroenterologist ([name] or [name]) via endoscopic approach under monitored and controlled anesthesia. Esophagogastroduodenoscopy (EGD) is very safe and routine diagnostic approach for adolescents with gastrointestinal disorders.[25] The balloon will remain in the stomach if tolerated for 6 months, and then it will be removed endoscopically by a gastroenterologist ([name] or [name]). In order to prepare for the IGB removal, the subject will need to be on a liquid diet for 48 hours prior to its removal, and consume nothing by mouth for at least 12 hours prior to the IGB removal. Subjects will be informed that the risk for complications increases after 6 months and that it is imperative that the balloon is removed at 6 months, otherwise the subject assumes the additional risks.

The multidisciplinary team consisting of a pediatric endocrinologist or pediatric gastroenterologist, and a dietitian at the weight management clinic, will evaluate the patient at baseline, at 3 and 6 months after the insertion of the balloon, and at 9 and 12 months, which would be after the removal of the balloon. The dietitian at the weight management clinic will review the PN Q and the food record template and guide the diet modification accordingly. Subjects will have follow up psychology visits to support adherence and address any emotional and social adjustment concerns. Blood and urine samples will also be collected at months 3, 6, 9 and 12, after the IGB insertion. The subjects and their parents will be contacted by phone by a GI nurse to answer telephone questionnaire in between the visits on site at 4 days, 2 weeks, and at months 1, 2, 4, 5, 7, 8, 10, and 11, after the IGB insertion.

Blood Samples: Eight to twelve hour fasting blood samples will be collected at baseline, 3, 6, 9, and 12 month visits including:

- CBC with differential
- Electrolytes panel (Sodium, Potassium, Calcium, Creatinine, Chloride, Bicarbonate, BUN)
- Liver function tests (AST, ALT, Alkaline phosphatase, Total Bilirubin, Total Protein, Albumin)
- Nutritional assessment (Fe/TIBC, B12, Folic Acid, 25-Hydroxy Vitamin D, Ferritin)
- Coagulation panel (ProTime/INR, PTT)
- Total Cholesterol/Lipid panel
- Thyroid function tests, PTH
- Insulin
- Glucose
- CRP
- HgA1c

The effect of the IGB on the GI physiology will be assessed by collecting the following GI hormones at baseline and at 3, 6, 9 and 12 months: Total Ghrelin; PYY; GLP-1; and Leptin.

In total, approximately 40 ml of blood will be drawn for all blood tests.

Urine Sample: A urine sample will be collected at baseline, 3, 6, 9, and 12 months.

Stool Sample: A stool sample will be collected for a fecal antigen study for Helicobacter pylori (H. pylori) (sensitivity > 96.8%) to exclude the presence of H. pylori prior to the initial endoscopic assessment.

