1.4 Clinical Data to Date

The Orbera™ Intragastic Balloon (Apollo Endosurgery, Austin, TX), previously known as the BioEnterics Intragastic Balloon (BIB) (Allergan, Irvine, CA) is an elastic spherical balloon made from silicone, filled with about 600 ml of saline and is placed in the stomach via upper endoscopy. This intragastric balloon (IGB) is designed to stay in place for 6 months prior to endoscopic removal and has been widely used in Europe, South America, and the Middle East with excellent safety profile. In an American Society of Gastroenterology and Endoscopy (ASGE) Bariatric Endoscopy Task Force systematic review and meta-analysis the pooled percentage of total body weight loss (TBWL) after the Orbera IGB implantation was 12.3% (95% CI, 7.91–16.73), 13.16% (95% CI, 12.37–13.95), and 11.27% (95% CI, 8.17–14.36) at 3, 6, and 12 months after implantation, respectively.[18] This was based on a review of 55 studies. This balloon is currently FDA approved for use in the United States after a US randomized multicenter pivotal trial demonstrated similar efficacy. There is paucity of data about the use of IGB in adolescents. Despite the preference for avoiding surgical and invasive intervention for managing morbid obesity in adolescents, high relapse rates of current approaches and minimal adverse events of IGB can justify this nonsurgical bariatric interventions.[19] A recent pilot study suggested that IGB was a feasible and safe intervention in obese adolescents resulting in weight loss and improvement in their metabolic syndrome. [17] Another important application to this intervention comes from the noticeable increase in the incidence NAFLD and NASH in adolescents is increasing, resulting in significant morbidity and long-term complications such as liver fibrosis and cirrhosis.[20] Neuman et al, suggested that bariatric procedures including noninvasive ones such as IGB intervention can resolve the liver involvement and prevent further complications.[21]

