4.4.2 Data Collection and Follow-up for Withdrawn Subjects

If a patient is withdrawn from the study for reasons other than severe adverse events, the IGB will be removed from the patient at a time that works for the patient and within 6 months of insertion. The patient will be followed as per the standard clinical protocol for the IGB to ensure safety. Weight and safety data will be collected until the IGB is removed. After IGB removal subjected will be followed clinically as per our protocol for additional six months to ensure safety.

5 Study Device

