5.4 Subject Compliance Monitoring

The Orbera IGB will be advanced to the stomach under endoscopy guidance and inflated with approximately 600 ml of normal saline. Subject transient nausea and pain symptoms will be managed with few days course of antiemetic and antispasmodics as per our clinical practice. Subject and their parents will then receive a phone call by a GI nurse at 4 days after the procedure (\pm 1 day), then 2 weeks (\pm 1 week), at 1 month (\pm 1 week), and monthly thereafter (\pm 1 week) when not being seen for a physical exam and in the weight management clinic at months 3, 6, 9, and 12 (\pm 1 week), per the clinical protocol visit schedule for the IGB as indicated on Table 2. The PI will evaluate all subjects if the GI nurse feels they need to be evaluated based on results of telephone questionnaire.

At 6 months (\pm 1 week), the subject will return for balloon removal at the pediatric endoscopy unit under monitored pediatric anesthesia care. During this visit, the subject will have blood samples drawn; a physical exam by pediatric gastroenterologist ([name]) or pediatric endocrinologist ([name]), followed by a meeting in the weight management clinic with the dietitian. Following the blood samples, PE, and WMC, the balloon will be removed at the same visit using the standard balloon retrieval kit approved by the FDA.

After balloon removal, all subjects will continue to be followed by the weight management team as indicated on Table 2. Weight, height, waist circumference, and demographic information will be collected at baseline, 3 months (\pm 1 week), time of balloon removal (6 months \pm 1 week), 9 months (\pm 1 week), and at 12 months (\pm 1 week).

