6.8 Schedule of Events

Table 2 provides a complete list of tests, procedures, and questions which will take place at each study visit, along with a time period and range for each study visit.

Table 2: Schedule of Events

Visit Type	Screening Visit	-4 weeks (+4 weeks)	-2 weeks (+2 weeks)	Day 0	Visit 0	4 days (± 1 day)	Visit 1	2 weeks (± 1 week)	Visit 2	1 month (± 1 week)	Visit 3	2 months (± 1 week)	Visit 4	3 months (± 1 week)	Visit 5	4 months (± 1 week)	Visit 6	5 months (± 1 week)	Visit 7	6 months (± 1 week)	Visit 8	7 months (± 1 week)	Visit 9	8 months (± 1 week)	Visit 10	9 months (± 1 week)	Visit 11	10 months (± 1 week)	Visit 12	11 months (± 1 week)	Visit 13	12 months (± 1 week)	Visit 14
Inclusion & Exclusion Criteria	x																																
Consent	x																																
Psychological exam		x													x					x									x				
Blood sample: GI hormones (2)		x												x				x		x					x			x			x		
Stool sample (3)		x												x																			
Urine pregnancy test (females) (4)				x																													
EGD/IGB insertion (1,4)				x																													
EGD/IGB removal (1,5)																			x														
Other Blood & Urine samples (6)		x												x				x		x					x			x			x		
PN Q (7)	x																														x		
CES-D & SCAS (7)	x													x																	x		
WMC		x												x				x		x					x			x			x		
PE (8)		x	x			x	x	x	x		x		x		x		x	x	x	x	x	x	x	x		x	x	x	x				
GI nurse telephone questionnaire					x	x	x	x	x	x	x	x	x	x	x	x	x	x	x	x	x	x	x	x	x	x	x	x	x				

Key:

EGD: upper endoscopy

IGB: Intragastric Balloon

PN Q: Pediatric Nutrition Questionnaire

CES-D: Self-Report Depression Scale Questionnaire

SCAS: Spence Child Anxiety Scale Questionnaire

WMC: Weight Management Clinic visit with dietitian

PE: Physical Exam by pediatric endocrinologist or pediatric gastroenterologist

Footnotes:

1-The IGB will be provided at no cost by the manufacturer.

2-GI hormones include: Total Ghrelin; PYY; GLP-1; and Leptin.

3-A stool sample will be collected for a fecal antigen study for H. pylori (sensitivity > 96.8%) to exclude the presence of H. pylori prior to the initial endoscopic assessment.

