4-Female subjects will have a urine pregnancy test in the morning before the IGB insertion. Once the pregnancy test is confirmed negative, then the IGB can be inserted. At this visit, the subject will also be given a wallet card with emergency information, as well as Mayo Clinic brochures regarding the upper endoscopy and intragastric balloon for weight loss.

5-At the 6 month visit, the subject will have blood samples drawn; a physical exam by the pediatric endocrinologist ([name]) or a pediatric gastroenterologist ([name]); and a meeting in the weight management clinic with the dietitian. Following the blood samples, PE, and WMC, the IGB will be removed at the same visit. The 6 month visit and balloon removal may all be completed in one day, or they may be completed on separate days depending on scheduling times and the subject's availability. This will be up to the discretion of the study team. In order to prepare for the IGB removal, the subject will need to be on a liquid diet for 48 hours prior to its removal, and consume nothing by mouth for at least 12 hours prior to the IGB removal.

6-Other tests include:

- CBC with differential
- Electrolytes panel (Sodium, Potassium, Calcium, Creatinine, Chloride, Bicarbonate, BUN)
- Liver function tests (AST, ALT, Alkaline phosphatase, Total Bilirubin, Total Protein, Albumin)
- Nutritional assessment (Fe/TIBC, B12, Folic Acid, 25-Hydroxy Vitamin D, Ferritin)
- Coagulation panel (ProTime/INR, PTT)
- Total Cholesterol/Lipid panel

- Thyroid function tests, PTH
- Insulin
- Glucose
- CRP
- HgA1c
- Urine sample

7-Questionnaires will be given to the subject after consenting to complete at home with a request that they be returned at the baseline visit. The PN Q will be returned to and reviewed by the dietitian at the weight management clinic. The CES-D and SCAS will be returned to and reviewed by the psychologist during the subject's psychological assessment. Any elevations in the CES-D and SCAS surveys will be further assessed during the subject's visit with the psychologist. If clinically indicated, additional psychological assessment and follow-up that may be needed and will be part of the subject's standard of care.

8-At the PE, the subject's height, weight, waist circumference, HR, BP, and demographics will be collected at baseline, 3, 6, 9 , and 12 months.

7 Statistical Plan

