- Unanticipated: (i.e. unexpected) problems or events are those that are not already described as potential risks in the protocol, consent document, not listed in the Investigator's Brochure, or not part of an underlying disease. A problem or event is "unanticipated" when it was unforeseeable at the time of its occurrence. A problem or event is "unanticipated" when it occurs at an increased frequency or at an increased severity than expected, **AND**

- Related: A problem or event is "related" if it is possibly related to the research procedures.

Adverse Event Reporting Period

For this study, the study treatment follow-up period is defined from enrollment in the study to 6 months after balloon removal (12 months from balloon insertion). Adverse events will be captured and reported from enrollment to the end of the study treatment follow-up.

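### Minor: the removal window lets the balloon stay up to 7 days past 6 months, although the protocol says complication risk rises after that point

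*Combined protocol and SAP*

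**What the plan says.** Section 3.1 (General Design) has subjects told that "the risk for complications increases after 6 months and that it is imperative that the balloon is removed at 6 months", and adds that a subject who does not comply takes on the extra risk. Section 1.4 says the balloon "is designed to stay in place for 6 months prior to endoscopic removal".

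Two other sections treat 6 months as the limit. Section 4.4.2 says that, for subjects withdrawn for reasons other than severe adverse events, the balloon comes out "at a time that works for the patient and within 6 months of insertion". Section 6.4 lists, among the grounds for early removal in the investigator's opinion, a subject who is moving and for whom removal at 6 months may not be achievable.

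The operating schedule is looser. Section 5.4 states: "At 6 months (\pm 1 week), the subject will return for balloon removal". The same section repeats the window for the measurements taken at "time of balloon removal (6 months \pm 1 week", and the Table 2 column that carries the removal is headed "6 months (± 1 week". Footnote 5 to Table 2 adds: "The 6 month visit and balloon removal may all be completed in one day, or they may be completed on separate days". It leaves the choice to the study team and names no latest removal date.

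**The concern.** A symmetric window suits a visit whose purpose is measurement, where a week either way matters little. Removal is different, because by the protocol's own account risk rises on one side of the target date only. Under the present wording the team could book removal 5 days past 6 months and be on schedule, although the subject would already be beyond the point the protocol warns about. The subjects are aged 14 to 17, and the plan states no clinical benefit from the extra days.

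What is at stake is a small, avoidable exposure, and a mismatch between what families are told and what the schedule allows. Sample size, error rates and the weight-loss endpoint are not affected.

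**Working it through.** The plan gives no figure to reproduce here, so the check sets the limits side by side and does the date arithmetic.

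**Inputs**
- Removal window for completing subjects: 6 months, minus 7 to plus 7 days (section 5.4; Table 2).
- Limit for subjects withdrawn for reasons other than severe adverse events: 6 months, plus 0 days (section 4.4.2).
- Length of 6 calendar months: 181 to 184 days, depending on the start date.
- Complication rate by time in place: not given.

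**Latest removal that is still on schedule**
- Completing subject: 181 + 7 = 188 days, to 184 + 7 = 191 days.
- Withdrawn subject: 181 to 184 days.
- Difference: 7 days.

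**Relative excess for a completing subject at the limit**
- 7 / 184 = 3.8%.
- 7 / 181 = 3.9%.

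**Effect of a minus 1 week / plus 0 window**
- Latest removal: 6 months, 0 days over, which matches section 4.4.2.
- Earliest removal: 6 months minus 7 days, as now. The minimum time in place does not change.
- Scheduling span: from 7 + 7 = 14 days to 7 days.
- Average time in place, assuming removals spread evenly over the window: the mean offset is (−7 + 7) / 2 = 0 days now and (−7 + 0) / 2 = −3.5 days after the change. Taking 6 months as about 182 days, 3.5 / 182 = 1.9% shorter.

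**Which date the window governs**
Footnote 5 allows the month-6 visit and the removal to fall on separate days. If the window applied only to the visit, removal could fall later than day +7. Section 5.4 attaches the window to removal itself, so day +7 is the better reading, but footnote 5 does not say so.

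**The case against.** The strongest reply is that "the risk for complications increases after 6 months and that it is imperative that the balloon is removed at 6 months" is counselling for families who might not return, and sets no day-level limit on the investigator. On this view 6 months is a nominal visit label: every contact from 2 weeks onward carries plus or minus 1 week, and section 6.7 has removal follow a completed 6 months. This explains the wording, and it means the sections do not flatly contradict each other. It does not explain why a step the protocol calls time-critical has the same two-sided tolerance as a measurement visit.

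The comparison with section 4.4.2 is supportive only. Withdrawn subjects have left the visit schedule and need some outer date, so a reader should not infer that the protocol deliberately holds them to a stricter safety standard.

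The need for flexibility is real. Removal is an endoscopy under anesthesia, and footnote 5 cites scheduling and subject availability. A window of 7 days still leaves room, at some cost. Omeprazole continues for as long as the balloon is in place (section 6.2), which gives some cover against acid injury in an extra week.

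The reply is also right that harm is not shown. Section 5.3 ties use of the device to the Orbera premarket approval, which is not available here, so any labelled tolerance cannot be checked.

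**Conclusion.** The point holds as a minor safety improvement. On-schedule removal can be up to 7 days past 6 months, or 3.8% to 3.9% longer in place, for a device whose complication risk the protocol says increases after 6 months. The 7 days follow directly from section 5.4 and Table 2, and the percentage assumes only that 6 months is 181 to 184 days. The added risk per day is not given and is probably small.

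Two stronger readings are tempting, and the documents support neither:
- **That the extra week exposes subjects to material harm or undermines the safety analysis.** No complication rate by time in place is given, so the documents cannot show this.
- **That late removal cuts short adverse event capture.** Section 8.1 ends the period at "6 months after balloon removal (12 months from balloon insertion". The two dates differ when removal is late, but the first of them moves with removal. Section 8.2 also has serious events after the study period recorded and reported if they are at least possibly related. Any shortfall at the month-12 visit is marginal and comes partly from that visit's own window.

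**What to change.** In section 5.4 and Table 2, set the balloon removal window to 6 months, minus 1 week / plus 0 days. In footnote 5, state that a removal on a separate day must observe the same latest date, and that the month-6 blood samples, physical examination and weight management visit must be done before it.

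Ask the team to schedule with enough margin to rebook a postponed removal within the limit, allowing for the 48-hour liquid diet in section 6.7. A fixed early booking rule, such as day −7 to day −3, is not advisable. It would routinely take every balloon out before the 6-month period named in the first Specific Aim.

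If the premarket approval allows a tolerance past 6 months, the sponsor could instead cite it and align sections 3.1 and 4.4.2 with it.

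The cost is mainly wording. The scheduling span halves, and average time in place falls by about 3.5 days if removals spread evenly. A removal that slips past 6 months would become a deviation, and section 8.3.2 requires prior approval for non-emergency deviations, so a few more may need handling. No procedure is added.

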8.2 Recording of Adverse Events

At each contact with the subject, the investigator must seek information on adverse events by specific questioning and, as appropriate, by examination. Study subjects will be routinely questioned about adverse effects at study visits. Information on all adverse events should be recorded immediately in the source document, and also in the adverse event log. All clearly related signs, symptoms, and abnormal diagnostic, laboratory or procedure results should be recorded in the source document.

All adverse events occurring during the study period must be recorded. All observed or volunteered adverse effects (serious or non-serious) and abnormal test findings, regardless of the treatment group if applicable or suspected causal relationship to the investigational device or if applicable other study treatment or diagnostic product(s) will be recorded in the subjects' case history. For all adverse effects sufficient information will be pursued and obtained as to permit; an adequate determination of the outcome, an assessment of the causal relationship between the adverse effect and the investigational device or, if applicable other study treatment or diagnostic product. The clinical course of each event should be followed until resolution, stabilization, or until it has been ultimately determined that the study treatment or participation is not the probable cause. Serious adverse events that are still ongoing at the end of the study period must be followed up, to determine the final outcome. Any serious adverse event that occurs after the study period and is considered to be at least possibly related to the study treatment or study participation should be recorded and reported immediately.

Adverse events will be solicited at each study visit or contact with patient. All adverse events will be recorded with the following information:

- Subject Study Number/Identifier
- Device information (model and serial number)
- Date of event onset
- Description of the event
- Indication if study treatment was discontinued, or if investigational device was removed
- Subject current status, or if the event was resolved
- Principal Investigator assessment of if the event was serious and justification for determination
- Principal Investigator assessment of causality and relationship to study treatment.

8.3 Sponsor-Investigator Reporting of Unanticipated Adverse Device Effects and Unanticipated Problems

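### No scheduled contact is timed from balloon removal: the first call after a month-6 removal comes about 30 days later, against day 4 after insertion

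*Combined protocol and SAP*

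**What the plan says.** - **Calls.** Section 3.1 schedules the nurse calls "at 4 days, 2 weeks, and at months 1, 2, 4, 5, 7, 8, 10, and 11, after the IGB insertion". Sections 5.5 and 9.3 give the same time points. Section 5.4 describes the first as a "phone call by a GI nurse at 4 days after the procedure", with a window of ±1 day, where the procedure is balloon placement.
- **Removal.** At 6 months (±1 week), "the subject will return for balloon removal at the pediatric endoscopy unit under monitored pediatric anesthesia care" (5.4). The order that day is fixed: "Following the blood samples, PE, and WMC, the balloon will be removed at the same visit". Footnote 5 to Table 2 keeps that order and lets the visit and the removal fall on separate days.
- **Next contact.** Table 2 goes from the 6-month column to the 7-month column (±1 week) with nothing between.
- **Procedure risks.** Section 1.5.2 states: "Possible risks which may occur from the subject's endoscopy procedure include difficulty swallowing, injury to the lining of the esophagus or stomach, perforation". It goes on to name bleeding, infection and pain that might need a hospital stay.
- **Collection of events.** Section 8.2 says: "Adverse events will be solicited at each study visit or contact with patient". It also records events that are observed or volunteered. Table 3 in 9.3 names the medical record as a source alongside the telephone questionnaire. Section 8.1 runs the reporting period to 6 months after removal.
- **Follow-up tied to removal.** Sections 1.5.2 and 6.5 follow subjects with an ulcer or device-related event present at removal. Section 4.4.2 gives withdrawn subjects six further months of clinical follow-up after removal, without contact dates.

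**The concern.** Insertion and removal are both endoscopic procedures, and the general endoscopy risks in 1.5.2 apply to each. After insertion, someone asks the family about events within days. After removal, nobody is scheduled to ask for about a month. An event that is new after removal is not covered by the follow-up in 1.5.2 and 6.5, which starts from a finding already present.

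Safety is part of the primary objective, and the first specific aim is to learn whether a 6-month placement is safe. With 12 subjects, a single event that is missed, misdated or learned of late can alter the safety description. Timing also matters for oversight: section 8.6.1 has the monitoring board review serious events within one week of occurrence, which presupposes that the study team knows of them.

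**Working it through.** The plan states no figure for this interval, so there is none to reproduce. The check is date arithmetic.

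**Inputs**
- Month length: 365.25 / 12 = 30.44 days.
- Removal: 6 months ± 7 days (5.4, Table 2).
- First later contact: 7 months ± 7 days (3.1, 5.4, Table 2).
- Calls after insertion: day 4 ± 1, week 2 ± 1 week, month 1 ± 1 week (5.4).

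In the text copy available, the row marks of Table 2 are not aligned with its columns. The schedule is therefore taken from the prose of 3.1, 5.4, 5.5 and 9.3 and from the table's column headings, which agree.

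**Gap after a month-6 removal**
- Nominal: 7 × 30.44 − 6 × 30.44 = 213.1 − 182.6 = 30.4 days.
- Shortest (removal late, call early): 30.4 − 7 − 7 = 16.4 days.
- Longest (removal early, call late): 30.4 + 7 + 7 = 44.4 days.

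| | After insertion | After removal |
|---|---|---|
| First scheduled contact | day 4 (3 to 5) | day 30 (16 to 44) |
| Scheduled contacts in the first month, nominal dates | 3 (day 4, week 2, month 1) | 1 (month-7 call) |

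**Does the month-6 visit close the gap?** No. Its assessments precede removal, so they cannot record what removal causes.

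**Early removal.** Section 4.4.2 promises clinical follow-up but sets no contact times. Section 8.1 equates 6 months after removal with 12 months from insertion, which is true only when removal falls at month 6. The first contact after an early removal therefore cannot be dated from the documents.

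**Oversight timing, conditional.** If a serious event on the day of removal first became known at the month-7 call, the one-week review limit would already have passed by at least 16.4 − 7 = 9.4 days.

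**Illustration on assumed values only.** Let p be the chance of a removal-related event per subject and s the share of such events recorded. The chance of recording at least one event in 12 subjects is 1 − (1 − p·s)^12.

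| p | s = 1 | s = 0.9 | s = 0.7 | s = 0.5 |
|---|---|---|---|---|
| 2% | 21.5% | 19.6% | 15.6% | 11.4% |
| 5% | 46.0% | 42.5% | 34.8% | 26.2% |
| 10% | 71.8% | 67.8% | 58.1% | 46.0% |

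The documents give neither p nor s for removal, so this shows only how the result depends on s.

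**With calls at day 4 and week 2 after removal:** the first contact falls at day 4 (3 to 5), and the first month holds 3 contacts instead of 1.

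**The case against.** The strongest reply is that a late question is not a missing question. The month-7 call lies inside the reporting period and asks about events. Volunteered events are recorded, and the medical record is a named source. The serious events listed in 3.4, such as perforation, bleeding or pain needing admission, usually bring a patient to care and are not readily forgotten in a month. Two of the primary safety endpoints, early intolerance leading to removal and balloon deflation, cannot arise after removal. The early calls after insertion also have a reason: transient nausea and pain are expected then, and 1.5.2 ties them to the balloon's presence, which removal ends.

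Most of this stands, and it limits the point. A reader might infer any of the following, and the documents do not support them:

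- *That removal-related events are necessarily under-counted.* The other capture routes make this a risk, not a certainty, and no detection rate is given.
- *That a comparison of on-balloon and post-removal event rates is biased.* No such comparison is planned; section 7 calls the results largely descriptive.
- *That no contact can occur within 28 days of removal.* This is so at nominal dates, but the windows allow a call as early as day 16.
- *That subjects with early removal simply stay on the insertion calendar.* No section says so, and 4.4.2 counts six months of clinical follow-up from removal.

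What the reply does not answer is that the routes available before month 7 are passive. The documents do not say how records of care received elsewhere would be obtained, and the insertion rationale does not cover the endoscopy risks that removal carries as well.

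**Conclusion.** The point holds as a cheap improvement. No scheduled contact is timed from removal, and the first after a month-6 removal is nominally 30 days later (16 to 44), against day 4 (3 to 5) after insertion. New removal-related events may be detected late, poorly dated or incompletely in the meantime. The weakness falls mainly on milder events and on those treated outside the institution; the latter is an inference. The gap rests on the stated schedule and windows and on removal at month 6. The size of any loss cannot be derived from the documents.

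**What to change.** In 3.1, 5.4, 5.5, Table 2 and 9.3, add the existing nurse telephone questionnaire at 4 days (±1 day) and 2 weeks after the **actual** removal date, whether removal is early or at month 6. This also supplies the contact dates that 4.4.2 lacks. In section 7, tabulate adverse events by period: insertion to removal, the first 28 days after removal, and later.

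Cost: 2 calls × 12 subjects = 24 calls, assuming one removal each, with the nurse and questionnaire already in place. No visit, procedure or subject is added, and treatment is unchanged. The reported post-removal event count may rise slightly because someone is asking sooner.
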